8.2 Vital Signs

Vital signs will be taken in the supine position at Baseline (pre-dose), at the completion of drug infusion, and at 24 Hours, 48 Hours and Day 5/discharge. Vital signs including temperature, systolic and diastolic blood pressure, heart rate, and weight will be

reported by assessment time. Absolute values and changes for vital signs from pre-dose to Day 5 or discharge will be documented. The maximum deviation of BP from Baseline between drug and placebo control groups (systolic and diastolic) to 24 Hours will each be analyzed using ANCOVA, including factors for treatment group, the use of general anesthesia and treatment with intravenous alteplase, three factors that may affect blood pressure. Results will be tabulated and listed by treatment group and timepoint.

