8.7.1 Immunogenicity Sample Collection

At Day 1 (24 hours post dose – a time when no significant quantities of NA-1 remain in the blood) and Day 30 a 5 mL sample of blood will be collected in tubes provided by the Sponsor. Sample collection method should be the least invasive to the subject and may be combined with routine blood sampling.

The samples will be handled per guidelines/instructions provided by the sponsor. These tubes are labeled with adhesive labels that identify the study code, site number, the subject's number, and the sample Day. A minimum of 1.0 mL of plasma will be transferred into each cryovial.

The date and time for each step (blood draw, storage, centrifugation, aliquoting, and freezing) and the number of aliquots obtained must be documented in the source document.

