10.2.3 Increases in Histamine

NA-1 has undergone preclinical testing in rats, dogs, rabbits, and non-human primates. When administered in these animals at doses higher than the one proposed in the current clinical trial, NA-1 has produced apparent anaphylactoid events characterized by histamine release in rats and dogs. The observed signs and symptoms were compatible with the physiological effects of histamine; specifically, transient hypotension and hives. This raises the possibility that anaphylactoid reactions to NA-1 could occur in humans. Patient susceptibility to drug-induced anaphylactoid events is highly variable. Therefore, potentially severe anaphylactoid reactions to the study drug may be encountered. Anaphylactoid reactions, including histamine-related reactions such as urticaria, bronchoconstriction, or hypotension, should be monitored. In the event that an anaphylactoid reaction requiring treatment occurs, treatment should follow the same algorithms as would be followed if a spontaneous anaphylactoid reaction occurred in the community.

- Follow emergency medicine ABCs and establish airway first.
- Treat hypotension with crystalloid, colloid and/or vasopressors as needed (see [Section 10.2.2](#)).
- Consider treatment with antihistamine agents (diphenhydramine 50 mg IV, ranitidine 50 mg IV) and corticosteroids if the reaction is severe.
- Consider using subcutaneous or intravenous epinephrine.
- If bronchospasm or laryngospasm are important symptoms, consider treatment with inhaled racemic epinephrine.

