11.9.4 Vital Signs

Absolute values and changes for vital signs from pre-dose to Day 5 or discharge will be documented. The maximum deviation of BP from Baseline between drug and placebo control groups (systolic and diastolic) to 24 Hours will be analyzed using ANCOVA, including factors for treatment group.

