While the artery remains occluded, systolic blood pressure (SBP) 150 or greater is probably useful in promoting and keeping collateral flow adequate. Indirect evidence supports this assertion. Once reperfusion has been achieved, BP often falls naturally. Controlling BP once reperfusion has been achieved aiming for a normal BP for that individual is sensible. Labetalol or an intravenous β -blocker such as metoprolol in low doses is preferred.

Keep complication rate low:

Be prepared to stop and back out. Do not take unnecessary risks. Remember that you do not necessarily need a “perfect” angiographic outcome to have a good clinical outcome.

Medical Management:

Designate one person to observe and manage the subject’s vital signs. Follow the oxygen saturation (SaO₂), pulse and BP. Manage accordingly. In an ideal circumstance, an anesthetist helps manage this aspect of care.

In the absence of an anesthetist, the standard of care is that the attending neurologist or stroke fellow will have a lead apron on and be in the neuro-angiosuite managing the medical and neurological condition of the subject.

BP management is described above. There are no clear guidelines that are based upon level 1 evidence.

Conscious Sedation Management:

We strongly recommend that all sites avoid general anesthesia. The vast majority of endovascular stroke treatment can be completed under conscious sedation. Several case series support the

concept that general anesthesia is associated with poorer outcomes. A possible explanation is prolonged BP lowering resulting in more rapid progression to infarction.

A simple conscious sedation paradigm for adult subject is as follows:

- 2.5 mg midazolam IV
- 25-50 µg fentanyl IV

These drugs should be given together since this avoids the occasional paradoxical agitation seen with intravenous benzodiazepines alone. They can be given q10-15min. Follow the RR and SaO₂ to avoid trouble with respiratory suppression. Managing conscious sedation can be done by the neurologist or stroke fellow in the room.

It is often additionally helpful to pre-treat subject with anti-nausea agents:

- 25-50 mg dimenhydrinate (gravol) IV [available in Canada, not the US]

This drug is very mildly sedating and may help avoid an episode of aspiration.

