All subjects, investigators, their clinical staff, the clinical coordinating center, the data management group, and the sponsor staff and delegates will be blinded to the randomization codes. The local laboratories will also be blinded.

Table 1. Schedule of Assessments

++	Baseline	Post- EVT (~2 h)	Day 1 (24 ± 12 h from random- ization)	Day 2 (48 ± 8 h from randomization)	Day 5 or discharge (±1 d)	Day 30 (±5 d)	Day 90 (±14 d)
Informed consent	X						
Attempt at regained capacity informed consent*			X	X	X	X	X
History and examination	X						
Weight	X*				X (Actual)		
Vital Signs (BP, HR, Temp) ★★	X	X	X	X	X		
Randomization/ Study drug administration	X						
Mortality					X	X	X
NIHSS	X	X	X	X	X	X	X
mRS			X¶		X	X	X
Barthel Index	X					X	X
BNT15, SNAP, MoCA¶¶							X
EQ-5D-5L						X	X
NCCT head	X						
CTA (Circle of Willis)	X						
Endovascular Procedure	X						
MR head			X**				
CBC, electrolytes, INR, aPTT, serum creatinine and serum glucose	X‡		X				
Pregnancy test	X‡‡						
Immunogenicity sample‡‡‡			X			X	
Pharmacokinetic samples‡‡‡‡	X						
ECG	X‡		X				
AE assessment	Collected to Day 30 visit						
SAE assessment	Collected to Day 90 visit						
Prior medications	X§§						
Concomitant medications	Collected to Day 30 visit						

* If the original process involved anyone other than the subject (and if required), site staff will make ongoing efforts until (1) regained capacity consent is obtained from subject, (2) death, or (3) completion of the Day 90 assessment.

★★ Vital signs (BP, HR only) should be recorded immediately before and after completion of the study drug infusion, temperature will be taken at baseline per standard of care. ¶ Historical (pre-stroke) score

¶¶ Assessments will be conducted only if the tool/scale is available in local language.

* At baseline estimated or actual weight

** Day 1 MR head may be supplanted by an NCCT head if MR is unavailable or contraindicated.

‡ ECG testing and Blood should be drawn at baseline, but results are not required prior to randomization. For ECG, if treating physician deems that pre-treatment ECG impedes access to timely care, ECG must be completed within 6 hours of randomization.

‡‡ If the subject is female and is of childbearing potential a pregnancy test (urine or serum point-of-care pregnancy test) must be completed and the result must be negative; this is the only mandatory laboratory test prior to randomization

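### The only tested blood-pressure outcome, an unsigned maximum deviation to 24 hours, can dilute a transient fall at the end of the NA-1 infusion

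*SAP*

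**What the plan says.** **The tested outcome.** Protocol 11.9.4: "The maximum deviation of BP from Baseline between drug and placebo control groups (systolic and diastolic) to 24 Hours will be analyzed using ANCOVA", with treatment group as the only listed factor. SAP 8.2 uses the same outcome, "The maximum deviation of BP from Baseline between drug and placebo control groups (systolic and diastolic) to 24 Hours", and adds general anesthesia and intravenous alteplase as factors. Baseline BP is not listed as a covariate in either. Neither document gives the sign of the deviation or the readings that feed it.

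**The readings.** SAP 8.2: "Vital signs will be taken in the supine position at Baseline (pre-dose), at the completion of drug infusion, and at 24 Hours, 48 Hours", and then Day 5 or discharge. Two post-baseline readings therefore fall within 24 hours. The footnote to SAP Table 1 says that BP and heart rate "should be recorded immediately before and after completion of the study drug infusion". The table itself marks vital signs in a Post-EVT (~2 h) column.

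**The risk.** Protocol 10.2.3 describes histamine-type signs in rats and dogs at doses above the trial dose: "specifically, transient hypotension and hives". In humans, decreased BP was an AE in 11% of Phase 1 subjects on any NA-1 dose (Protocol 4.4.1). Hypotension was reported in 6% on placebo and 10% on NA-1 in Phase 2 (Protocol 4.4.2).

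**The 24-hour reading.** Protocol 8.7.1 calls 24 hours post dose "a time when no significant quantities of NA-1 remain in the blood". Protocol Appendix 1, under Control BP, adds: "Once reperfusion has been achieved, BP often falls naturally".

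**Other BP reporting.** SAP 8.2 tabulates BP values and changes by arm and timepoint. SAP 8.1 tabulates special-interest AEs with onset 0-120 minutes after the end of infusion, and its Appendix 1 (Table A-2) includes hypotension terms. No test or interval is stated for either table.

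**The concern.** The stated BP risk is a short fall around a 10-minute infusion. Only one of the two readings entering the tested outcome is taken at that time. The other comes after the drug has cleared and also reflects reperfusion and BP care. Where the later change is the larger, it replaces the earlier one in the analysis, and the drug effect in that subject drops out.

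At stake is how a null result would be read. The plan tests BP once. If that test is insensitive to the stated risk, a non-significant result could be taken as reassurance about pressure at the time of exposure, which it would not provide.

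**Working it through.** **1. Figure to reproduce.** The plan gives no power, standard deviation (SD) or effect size for BP, so there is none. From the plan I use 560 per arm (SAP 1.4) and the two-sided 0.05 level (SAP 6.0). All BP inputs below are assumptions.

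**2. How two readings become one value.** Let x be the change at end of infusion and y the change at 24 hours. The text allows at least three outcomes:

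- Signed maximum: whichever of x and y is larger in size, with its sign.
- Absolute maximum: max(|x|, |y|).
- Largest fall: min(x, y).

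Two made-up subjects show the effect. With x = -20 and y = +25, the values are +25, 25 and -20. With x = -20 and y = -25, they are -25, 25 and -25. Only the largest fall in the first subject keeps the end-of-infusion value.

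**3. End-of-infusion change alone, true NA-1 fall of 5 mmHg.** SE = SD × √(2/560), and power = Φ(5/SE - 1.96).

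- SD 15: SE = 0.896, 5/0.896 = 5.58, power Φ(3.62), about 100%.
- SD 20: SE = 1.195, 5/1.195 = 4.18, power Φ(2.22) = 98.7%.

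**4. Pooled outcomes, same 5 mmHg fall.** x and y are bivariate normal and the NA-1 effect is placed on x only. Arm differences and SDs come from simulation (1,000,000 draws per arm), and power from the normal approximation at 560 per arm. In the first row below, the signed difference is -2.78 with SE about 1.61, so power is Φ(2.78/1.61 - 1.96), about 41%. The absolute difference is +0.35, and power is 7%.

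| SD x/y; correlation; placebo mean x/y (mmHg) | End of infusion | Signed | Absolute | Largest fall | 24 h sets the maximum (NA-1 arm) |
|---|---|---|---|---|---|
| 15/25; 0.3; 0/0 | 100% | 41% | 7% | 73% | 65% |
| 15/25; 0.6; 0/-20 | 100% | 22% | 6.5% | 11% | 76% |
| 20/20; 0.3; 0/0 | 98.7% | 68% | 8% | 73% | 49% |
| 20/20; 0.3; -10/-20 | 98.7% | 54% | 23% | 42% | 56% |
| 15/15; 0.6; -10/-10 | 100% | 89% | about 80% | 93% | 41% |

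Over the 16 scenarios with SDs of 15/25 or 20/20 (correlation 0.3 or 0.6, 24-hour mean 0 to -20), power is 22-68% signed, 5-23% absolute and 11-73% for the largest fall. The 15/15 row is the most favourable to the planned outcome and sets the upper ends of the overall ranges.

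**5. Larger or concentrated effects.**

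- A 10 mmHg fall, same 16 scenarios: 100% on the end-of-infusion change, 64-99.8% signed, 5-87% absolute, 41-100% largest fall.
- A 30 mmHg fall in 10% of NA-1 subjects (SD 15/25, correlation 0.3): 87%, 15-29%, 13-29% and 17-49% in the same order.

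**6. What this shows.** Pooling costs power under every reading of the term. Specifying a fall does not cure it, because the 24-hour value still enters.

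**Limits.** The simulation omits the general-anesthesia and alteplase factors and any baseline adjustment. It uses two post-baseline readings. A separate reading at about 2 hours would be a third input and would change the figures.

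**The case against.** The strongest reply is that an infusion-time fall is already reported by arm. SAP 8.2 gives BP changes by arm and timepoint, which includes completion of infusion. SAP 8.1 tabulates early hypotension AEs. Protocol 10.2.2 and 10.6 require hypotension and clinically significant post-dose vital signs to be recorded as AEs. The data monitoring committee sees unblinded AE data at 100, 300 and 600 subjects. A reader might infer from the tested outcome that a fall would be hidden from the trial report. The documents do not support that. What remains is that no between-arm test or interval is stated for those tables. A moderate mean fall also need not become an AE, because Protocol 10.2.2 defines hypotension as systolic below 80 mmHg or a decrease that the physician deems clinically relevant.

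A reader might also infer that the outcome was deliberately made undirected. The text is silent on sign, so the defect is an undefined term, and the loss depends on how it is later defined.

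The size can be challenged too. Making the 24-hour SD the larger builds in dominance by that reading, and with equal SDs of 15 the signed version reaches 89%. That stands, so it cannot be said that the 24-hour reading usually supplies the maximum or that the outcome mostly measures reperfusion.

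The prior evidence is limited. The animal signal arose above the trial dose, and the primate studies at 2.6 mg/kg (Protocol 4.3.1.2, 4.3.1.4 and 4.3.1.6) found no difference in mean arterial pressure. The human AE rates still make a fall the direction of interest.

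Finally, the primary safety outcomes are serious AEs and 90-day mortality, no decision rule depends on this ANCOVA, and dropping the 24-hour outcome would remove the only test of later change. These points favour adding a comparison over replacing one.

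**Conclusion.** The point holds in a limited form. The one BP outcome with a stated test has no defined sign, and it pools the reading at exposure with one taken after the drug has cleared. A transient NA-1 fall can be diluted in that test, or largely lost if the deviation is absolute.

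For a 5 mmHg fall at end of infusion and 560 per arm, power is about 99-100% on the end-of-infusion change, against roughly 20-90% on a signed maximum deviation and 5-80% on an absolute one. A 10 mmHg fall is usually still detected by the signed version. These ranges rest wholly on assumed means, SDs and correlations. The direction of the loss is firm and its size is not.

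This is an inexpensive improvement to a secondary safety analysis. It does not affect the primary safety or efficacy conclusions.

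**What to change.** In SAP 8.2 and Protocol 11.9.4:

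1. Add a pre-specified between-arm comparison (estimate and 95% CI) of the change in systolic and diastolic BP from pre-dose to completion of infusion, with a negative value meaning a fall. Adjust for baseline BP and for the general-anesthesia and alteplase factors that the SAP already names.
2. Give the between-arm difference in the rate of hypotension AEs with onset 0-120 minutes after the end of infusion, with a CI. SAP 8.1 already tabulates these events.
3. Keep maximum deviation to 24 hours as supportive, and state its sign and the readings that contribute.
4. Reconcile the Post-EVT (~2 h) vital-signs column with the table footnote and SAP 8.2, so that it is clear whether a separate reading exists.

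The pre-dose and end-of-infusion readings are already scheduled, so no new data are needed. The cost is wording in both documents, minor programming and one additional safety comparison.

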4.4.3 Summary of Safety of NA-1

Overall, NA-1 administered as a single intravenous dose was well tolerated at doses up to and including 2.6 mg/kg, and no safety concerns have been identified in any of the patient groups in the clinical trials.

4.5 Description of and Justification for the Route of Administration, Dosage, Dosage Regimen and Treatment Period

NA-1 2.6 mg/kg, up to a maximum of 270 mg (or matching placebo volume) is administered as a single approximately 10-minute intravenous infusion in the upper or lower extremity using an infusion pump initiated in the CT scan suite. The 2.6 mg/kg dose was chosen for this clinical trial because of (1) the safety profile observed in the previous Phase 1 and 2 clinical trials, (2) the observed capacity of this dose of NA-1 to reduce stroke tissue damage and to improve neurological function in rats and non-human primates exposed to experimental strokes when NA-1 was administered in animals exhibiting salvageable brain, and (3) the capacity of this dose to reduce stroke tissue damage and improve neurological damage in human subjects undergoing endovascular repair of brain aneurysms.

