The total imaging time starts from the time the subject reaches the door of imaging suite to when the subject is out of there and ready to move to next step. It includes putting subject on table, setting intravenous line, connecting to pump, etc. In the case of MR it would include the time taken to exclude presence of pacemaker etc. It includes post-processing time. Imaging time should not exceed 15 minutes.

Excellent overall organization to reduce CT-to-groin puncture time:

There are multiple steps to get from imaging to the groin puncture and these may include:

- Image interpretation
- Blood draw
- ECG
- Anesthesia involvement for conscious sedation
- Prepping the angiography suite
- Availability of nurse and technician
- Availability of respiratory technician and anesthetist if appropriate
- Ability to move the subject from the CT suite rapidly to the interventional suite

Groin puncture-to-recanalization time:

From the time the subject is on angiography suite table:

- Pre-plan your procedure, catheters required by reviewing the CTA of the arch
- Puncture the groin while the subject is getting draped. Do not wait.

- Have a stroke kit ready.
- Have a pre-decided division of labour: who is going to do what?
- Simple things like shaving the groin: is it needed?
- Foley catheter. Draining the bladder improves subject comfort and help reduce BP
- Assess need for anesthesia; overall general anesthesia should be avoided. Involvement of an anesthetist for conscious sedation is ideal.
- Training on use of other drugs to hold subject still: consult with local anesthetist.
- 8F sheath.
- Go straight to vessel of interest.
- Choice of catheter dependent on CTA.
- Whether common carotid artery run needed on not dependent on CTA.
- Try to use standardized microcatheter and wire.
- Plan an entire kit of stuff that is needed included things like a 60 cc syringe.

TICI2c or 3 flow:

Aim for complete recanalization [Thrombolysis in Myocardial Infarction (TIMI) 3] and reperfusion (TICI 3). A few small distal emboli are an acceptable outcome and are generally tolerated well by collateral flow.

Control BP:

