The only subject who typically will require intubation include those with paradoxical agitation associated with a Wernicke's aphasia, or those who develop respiratory compromise due to aspiration or other event arising after randomization.

Carotid artery stenting:

It is recommended as a guideline that carotid artery stenting is should not be done as part of the treatment in the study. Tandem occlusion of the extracranial carotid at the bifurcation associated with an M1-MCA occlusion is common. Patients with tandem occlusions are eligible for enrolment. The target lesion initially is the M1-MCA occlusion. Advance a catheter past the ICA lesion and deal with the M1-MCA first. Very often, in this process, the proximal ICA is open at the end of treating the M1-MCA because of the mechanical manipulation of the occlusive lesion at the carotid. What was initially a 99% stenosis is reduced to 60 or 70%.

At this point stop. Treat the subject with ASA per rectum (since they cannot swallow) and bring the subject back the following day to decide on whether subsequent procedures are necessary. It is simply not necessarily true that forward flow in the carotid is required to keep the M1-MCA open.

The major potential difficulty with leaving a carotid stent in place is the need for antiplatelet therapy, which will increase the chance of major symptomatic bleeding.

If, despite the above, the treating physician deems that a stent is required – either intracranially or at the carotid bifurcation because this action is in the patients' best interest, we recommend using ASA and clopidogrel rather intravenous abciximab or eptifibatide. Give ASA per rectum and as soon as possible give 600 mg clopidogrel per NG.

Use of IA medications:

Use of intra-arterial medication such as alteplase, abciximab, eptifibatide, tirofiban is not advised although nothing in this protocol forbids the use of any treatment that the treating physician deems to be in the subject's best interest. Any such medications will be noted in the CRF. Note that alteplase is not indicated for direct IA catheter delivery.

Number of Devices / GP2b3a Inhibitors / When to stop:

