7.4 Exploratory Analyses

In addition to the primary and secondary analyses adjusting for age, sex, baseline NIHSS score, baseline ASPECTS, intravenous alteplase, declared first device, occlusion location and site, exploratory subgroup analyses will be conducted to

determine whether any of these factors can modify the effect of the NA-1 vs. placebo treatments. Sub-group analyses will be performed on the primary outcome and include forest plots to display effect sizes by sub-group⁶.

Dichotomous sub-groups of interest include the following:

1. Age > 80 years of age
2. Sex (men vs. women)
3. Treatment with intravenous alteplase (yes/no)
4. Treatment by first declared thrombectomy device (Stent vs. Aspiration)
5. Subjects whose time from onset of stroke symptoms to NA-1 (or placebo) treatment was ≤ 6 hrs vs. > 6 hours.
6. Severe stroke defined as NIHSS > 20 vs. NIHSS ≤ 20 .
7. Outcomes by recognized ethnic and racial groups.
8. Outcomes by degree of reperfusion (TICI $\geq 2b$ vs. TICI $< 2b$)
9. General anesthesia vs. no general anesthesia
10. Baseline occlusion location (MCA vs. ICA)
11. Subjects whose time from onset of stroke symptoms to NA-1 (or placebo) treatment was ≤ 4 hrs vs. > 4 hours.
12. Subjects weighing between 105-120 kg.
13. ASPECTS score of 5-7 vs. 8-10

Additional sub-groups may be examined, but those specified above are of prior clinical interest.

Effect sizes will be estimated as subgroup-specific odds ratios ($\pm 95\%$ CIs) as follows. Separate logistic regression models for the primary endpoint, with treatment group and the stratification variables and covariates used in the minimization algorithm as predictors, will be fit to each of the subject subgroups (e.g., a model will be fit to males

and a second model will be fit to females). The estimated (NA-1/placebo) odds ratios, with 95% confidence intervals will be the NA-1 effect size estimates for each of the subgroups (e.g., for males and for females) and will be displayed in the forest plots.

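### The blood-pressure safety model in SAP 8.2 adjusts for general anesthesia, a post-randomization variable, so it does not estimate the total NA-1 effect on blood pressure if NA-1 changes anesthesia use

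*SAP*

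**What the plan says.** SAP 8.2 compares the arms on the largest systolic and diastolic deviation from baseline up to 24 hours, with an ANCOVA "including factors for treatment group, the use of general anesthesia and treatment with intravenous alteplase, three factors that may affect blood pressure". It does not restrict the anesthesia term to anesthesia begun before dosing, and it names no model without that term.

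Protocol 11.9.4 describes the same analysis more briefly: the deviation "to 24 Hours will be analyzed using ANCOVA, including factors for treatment group". Anesthesia is not mentioned there.

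On timing and cause, the protocol says:

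- Section 4.5: the infusion is given "using an infusion pump initiated in the CT scan suite".
- Appendix 1, in the list of steps once the patient is on the angiography table: "Assess need for anesthesia; overall general anesthesia should be avoided".
- Appendix 1, Conscious Sedation Management: patients who may need intubation include those with agitation, "or those who develop respiratory compromise due to aspiration or other event arising after randomization".
- Section 10.2.3: anaphylactoid reactions to NA-1, with bronchoconstriction or hypotension, are a possibility in humans. The first management step listed is "Follow emergency medicine ABCs and establish airway first".

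Section 6.2 stratifies by alteplase use and declared device and minimizes on six baseline variables. Anesthesia is in neither set. Section 6.7 lists its rate of use among the process metrics.

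**The concern.** A covariate in a randomized comparison should be fixed before treatment can influence it. Alteplase, as a stratification factor, meets that test. Anesthesia does not. Two routes could link it to study drug: a reaction may lead to airway intervention, or a pressure fall already recorded at the end of infusion may influence the later decision. On either route, the model compares arms within groups that treatment helped to form, and part of a drug-related fall can be credited to anesthesia.

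What is at stake is the reading of the one formal test of measured blood pressure. Hypotension has its own management section (protocol 10.2.2) and was reported in 6% of placebo and 10% of NA-1 subjects in the Phase 2 study (protocol 4.4.2). If NA-1 increased anesthesia use and anesthesia lowers pressure, the error would run toward no effect, which is the unhelpful direction for a safety analysis.

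**Working it through.** The plan states no effect size, SD or power for this analysis, so there is no figure to reproduce. Only the 560 subjects per arm (SAP 1.4) comes from the documents. Every other input below is an assumption.

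**1. Two-stratum example.** Assume that 10% of each arm has anesthesia unrelated to drug, with a 25 mmHg fall. A further 3% of NA-1 subjects have a reaction with a 40 mmHg fall, and a fraction f of those reactions leads to anesthesia. All others have no change.

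Unadjusted difference, for any f: 0.03 × (−40) = −1.20 mmHg.

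Adjusted difference = (w_G d_G + w_N d_N)/(w_G + w_N). Here d is the arm difference within the anesthesia (G) or no-anesthesia (N) group, and w = n1·n0/(n1 + n0), with n as a percentage of the arm.

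For f = 1:

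- d_G = (10×(−25) + 3×(−40))/13 + 25 = −3.46; w_G = 13×10/23 = 5.65
- d_N = 0; w_N = 87×90/177 = 44.24
- Adjusted = −3.46×5.65/49.89 = −0.39

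For f = 0.5:

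- d_G = (−250 − 60)/11.5 + 25 = −1.96; w_G = 11.5×10/21.5 = 5.35
- d_N = 1.5×(−40)/88.5 = −0.68; w_N = 88.5×90/178.5 = 44.62
- Adjusted = (−1.96×5.35 − 0.68×44.62)/49.97 = −0.81

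The same formula gives the other rows:

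| f | adjusted (mmHg) | lost (mmHg) | lost (%) |
|---|---|---|---|
| 0 | −1.20 | 0 | 0 |
| 0.10 | −1.13 | 0.07 | 6 |
| 0.25 | −1.01 | 0.19 | 16 |
| 0.50 | −0.81 | 0.39 | 32 |
| 1.00 | −0.39 | 0.81 | 67 |

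**2. Simulation with a different structure.** One million subjects per scenario: reactions in 2% to 10% of NA-1 subjects with a 40 mmHg fall, 10% background anesthesia, and anesthesia adding a further fall of 0 to 20 mmHg. The loss is about 0% if no reaction leads to anesthesia, 0–7% if 10% do, 0–12% if 25% do, and 2–26% if half do. For example, with 5% reactions, half leading to anesthesia, and a 20 mmHg anesthesia effect, the estimate is −2.49 without the term and −1.92 with it (23% lost).

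**3. Pure mediation.** The mmHg removed equals the excess anesthesia risk on NA-1 times the anesthesia effect. For an effect of 10 to 30 mmHg, this is 0 with no excess, 0.1–0.3 for a 1-point excess and 0.5–1.5 for a 5-point excess.

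**4. Scale.** The standard error of the arm difference is SD × √(2/560): 0.90, 1.20 and 1.49 mmHg for SDs of 15, 20 and 25. Every loss in the table is below 0.90. The largest simulated loss, 4.96 − 3.68 = 1.28 mmHg, falls inside the range 0.90–1.49.

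**The case against.** A reader might infer that the model does remove part of the NA-1 effect, perhaps two thirds of it. The documents do not support that, for these reasons:

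- **No passage says that NA-1 changes anesthesia use.** Appendix 1 speaks of aspiration or another event and does not name study drug. The airway step in 10.2.3 is general emergency guidance and does not mention anesthesia. The anaphylactoid findings are from rats and dogs at higher doses. Phase 1 had no SAEs, and no Phase 2 SAE was judged drug-related. The link is an inference.
- **Dosing before anesthesia is the usual planned order, not a rule.** Protocol 10.2.1 allows dosing to overlap the procedure.
- **Two thirds is an extreme case.** It needs every reaction to lead to anesthesia and no drug effect in anyone else. Add a 3 mmHg direct fall in all NA-1 subjects and the loss at f = 1 becomes 0.81/4.20 = 19%.
- **The readings may miss the anesthesia effect.** The text of SAP 8.2 and protocol 8.11 and 10.6.1 places readings up to 24 hours at baseline, end of infusion and 24 hours. Only the schedule tables mark a post-procedure reading. If none of the anesthesia fall is captured, f = 1 gives (−120/13 × 5.65)/49.89 = −1.05, a 13% loss.
- **A hypotension signal would not be hidden.** SAP 8.1 tabulates events of special interest by arm within 120 minutes of the end of infusion, with no anesthesia adjustment described. Appendix 1 of the SAP includes hypotension terms and endotracheal intubation. Vital signs are also summarized.
- **The term has a rationale.** The protocol itself links general anesthesia to prolonged pressure lowering, and anesthesia is not balanced by design.

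These arguments limit the size and likelihood of harm, and all of them stand. They do not make the adjusted coefficient an estimate of the total drug effect. The event tables count reported events and do not test measured pressure. Chance imbalance in elective anesthesia affects precision and does not bias the unadjusted comparison. The protocol's wording is brief and not exclusive, so adding a covariate in the SAP is not in itself an error; the fault is that the added covariate is measured after randomization.

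**Conclusion.** The point holds, conditionally, and is minor. The main blood-pressure model conditions on a post-randomization variable. If NA-1, or a fall it causes, alters anesthesia use, the treatment coefficient is not the total effect and can be pulled toward zero. If it does not, the term is harmless in expectation and may add precision. The trial cannot know in advance which applies, and that is the reason not to rest the main model on it.

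On assumed inputs the loss is 0% with no effect on anesthesia use, about 6% to 32% when 10% to 50% of reactions lead to anesthesia, and about two thirds when all do. In most scenarios it is below one standard error. These figures depend on assumed anesthesia rates, reaction rates and pressure falls.

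The objection does not reach the alteplase term. The subgroup "General anesthesia vs. no general anesthesia" in SAP 7.4 is a separate exploratory efficacy analysis and adds nothing to this point.

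**What to change.** In SAP 8.2, make the main ANCOVA treatment plus the alteplase stratum. Keep the anesthesia-adjusted model as a sensitivity analysis, labelled as adjusting for a post-randomization variable. Report anesthesia use by arm, with its timing relative to the infusion if recorded. Reconcile the model statement with protocol 11.9.4.

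The cost is a short SAP edit and possibly a little precision. With the assumed 10% anesthesia rate and 25 mmHg effect fully captured, the variance left in the residual is 0.10 × 0.90 × 25² = 56. Against a residual SD of 20, the standard error grows by a factor √((400 + 56)/400) = 1.07. It grows less if the reading times miss part of the anesthesia effect.
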